(1) *Test the effects of free FV provision on:* (a) household food waste levels (mass/grams and energy/kilocalories), (b) total FV acquisition (free FV provision plus purchases post-intervention vs. pre-intervention FV purchases), and (c) the consumption of FV (Food Patterns Equivalents Database, FPED). We hypothesize that free FV provision will increase food waste, total FV acquisition, and diet quality (increase the Healthy Eating Index [HEI]). We will test these hypotheses by comparing baseline and follow-up data from participants randomly assigned to the control condition, which features free FV provision and a placebo (stress management) intervention not focused on food waste. Exploratory analyses will examine the effects on dietary energy intake and if the freely provided FV replace non-FV foods in the baseline diet.

(2) Test if a smart intervention to reduce food waste and replace less healthy foods with FV significantly reduces post-intervention food waste compared to the control group while increasing FV acquisition and consumption compared to pre-intervention baseline. We hypothesize that this smart intervention will increase total FV acquisition and FV consumption compared to baseline, and these increases are not expected to differ significantly from control. It is further hypothesized that those receiving the smart intervention will significantly reduce food waste compared to controls. Exploratory analyses will examine the extent to which the smart intervention had the intended effect of replacing less healthy foods with FV consumption.

Background

The most recent Dietary Guidelines (Dietary Guidelines Advisory Committee 2015; at time of grant submission) ² recommend a dietary pattern featuring greater consumption of FV to reduce the risk of cardiovascular disease, type-2 diabetes, some cancers, and obesity, whose prevention would yield numerous health and economic benefits ³. Despite extensive public messaging and well-documented evidence of health and economic benefits, only about 10% of Americans eat the recommended amounts of FV ⁴ with the high cost of FV identified as one barrier to increasing FV intake ^{5 6}.

Given that FV are the most wasted food category and that FV subsidies have regularly been shown to increase FV expenditures but not consistently been shown to increase FV intake ^{7 8}, additional research is needed to:

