At Visit 1, participants will come to PBRC and will provide informed consent. Post consent, the participant's height, weight, and BMI will be measured and recorded. Participants will install and learn how to use the FoodImage app. They will complete a baseline questionnaire including questions about demographics, SNAP eligibility, and socioeconomic variables. They will also complete a Household Needs Survey to obtain the height, age, activity level and weight of household members as well as any allergies, intolerances, and food related restrictions in the household. They will also complete a Fruit and Vegetable Preference Survey (FV Preference Survey) to let researchers know which fruits and vegetables can be included in each household's box. If the participant begins to express fatigue or the PBRC employee performing the visit deems it necessary, the surveys can be sent to the participant via email through REDCap¹³. Participants should complete the surveys within 24 hours of Visit 1 and a PBRC employee will follow-up with the participant if the surveys are not completed during this time. If a mistake is made or questions are unintentionally omitted, a PBRC employee will call the participant within 24 hours to collect the remaining data and/or participants will fill out surveys at Visit 2. Participants will also receive instruction on how to conduct a fridge and cabinet cleanout and how to conduct a household Fruit Vegetable inventory. Following Visit 1, participants will collect data in a free-living environment over the course of approximately 1 week. To prepare for home data collection, participants will be asked to clean out their fridge, freezer and cabinets of any items that need to be discarded. After the cleanout is conducted, the participant will complete a video home inventory of all fruits and vegetables including fresh, frozen, & those otherwise preserved. This fruit and vegetable inventory will be conducted via a Microsoft Teams video call with a study staff member. This video call will be recorded and stored for data analysis purposes. During the call, the participant will perform the home Fruit and Vegetable Inventory guided by the study staff member; the study staff member will ask probing questions to ensure all fruits and vegetables have been shown. Following the

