call, the study staff member will complete data entry for the fruits and vegetables inventoried on the call. Participants will also complete baseline data collection using the FoodImage app to record food acquisition (Shop), food prep (Prep), intake (Eat) and waste (Toss) for approximately 3 (24 hour) days; ideally including 1 weekend date.

At Visit 2, participants will be randomized, as described in the analysis section, to one of two groups: A Food Waste & Substitution Group (Treatment Group) or a Stress Management Group (Control Group). Both Groups will receive their first fruit and vegetable box, will complete a lifestyle interview, and will receive their first group specific intervention visit.

Participants in the **treatment group** will meet individually with a trained coach who presents a set of materials that includes an introduction of food waste, ways that food waste can be reduced over time, and how to increase FV consumption by replacing consumption of less healthy foods with FV. The coach and participant then discuss the participant's lifestyle, including things like typical eating, shopping, prepping, storage, and meal habits. They also may discuss things like the number of people in the household, number of shopping trips, meal planning (or lack thereof), etc. The coach and participant will then tailor actions to most effectively reduce food waste and increase FV intake. In ensuing sessions, steps are made to follow up on plans and to introduce new plans to reduce food waste and increase fruit and vegetable intake. Between these in-person sessions, the interventionist will check in with the participant to follow-up on their progress. These check-ins can occur via phone, video chat, etc. To identify ways in which such interventions can be improved and to facilitate intervention fidelity and internal validity, some sessions with participants will be recorded. These recordings will be reviewed by the study team, namely Drs. [name], [name], and [name].

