Participants will return weekly for Visits 3 & 4 where they will receive FV boxes and will continue with intervention.

Fruit and vegetables for visits 2-4 will be procured on Tuesday afternoons. Ideally the participants will come in on Wednesdays to pick up their box and receive intervention. If needed, the participants can come to the center on Thursday to receive their box and intervention. In extenuating circumstances, the box and intervention may be delivered at the participant's home. If none of the previous options work, the participant may receive their box or intervention on Friday, but the fruit and vegetables will need to be checked for deterioration and replaced as needed.

In the week following Visit 4 participants will continue intervention, consume their last box of fruit and veg, and will collect their follow up time point of data collection where they will use the FoodImage app to record food acquisition (Shop), food prep (Prep), intake (Eat) and waste (Toss) for approximately 3 (24 hour) days; ideally including 1 weekend date.

The day before Visit 5, the participant will again complete a video home inventory of all fruits and vegetables including fresh, frozen, & those otherwise preserved. This fruit and vegetable inventory will be conducted via a Microsoft Teams video call with a study staff member. This video call will be recorded and stored for data analysis purposes. During the call, the participant will perform the home Fruit and Vegetable Inventory guided by the study staff member; the study staff member will ask probing questions to ensure all fruits and vegetables have been show. Following the call, the study staff member will complete data entry for the fruits and vegetables inventoried on the call.

At Visit 5, participants will complete either the Food Waste Exit Survey or the Stress Management Exit Survey, based on their randomized group and a final height, weight and BMI will be measured.

Schedule of Procedures

Figure 1: The schedule of procedures is outlined below:

Study Day	Visit & Timing	Participant Activity	
Prior to D -15*		Respond to recruitment, qualify for study and schedule study staff phone call.	
-15*	Study Call (~0.5 hours)	Call with study staff to determine if study is a good fit.	

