-8*	Visit 1 (~3 hours)	Attend training @ PBRC to: 
 • Provide informed consent. • Measure height weight and BMI. • Complete Baseline Survey (demographics, including SNAP eligibility assessment, socioeconomic variables), FV Preferences Survey, and Household Needs Survey (self-reported demographics, allergies, intolerances, and restrictions for household members). If desired or deemed necessary by the participant or the PBRC employee conducting the lab visit, surveys may be done after the appointment via REDCap. • Learn how to conduct household FV inventory. • Install and learn how to use the FoodImage app. 	
-8*	Day of* V1	Conduct a video home inventory of all Fruits & Vegetables (fresh, frozen, or otherwise preserved) via Microsoft Teams Call with study staff member.	
-7 - -1*	Week* following V1	Baseline Data Collection Use FoodImage to record food acquisition (Shop), food prep (Prep), intake (Eat) and waste (Toss). 
 • For approximately 3 (24 hour) days (ideally including 1 weekend date) use FoodImage to record all food acquisition (Shop), food prep (Prep), intake (Eat) and waste (Toss). 	
0	Visit 2 ~ +7* days from V1 (~ 3 hours)	Treatment Group Food Waste & Substitution 
 • Receive fruit and vegetable box. • Lifestyle Interview • Begin Intervention 	Control Group Stress Management 
 • Receive fruit and vegetable box. • Lifestyle Interview • Begin Intervention
0-7*	Week* following V2	Interventionist will check in with ppt goals and will send group specific nudges via participant's preferred form of communication between V2 and V3.	

0-35*	Ongoing until end of study	Use FoodImage to record food acquisition (Shop) & food waste from storage clean outs (Toss); continue interacting with PBRC staff on respective interventions.
8*	Visit 3 ~ +7* days from V2 (~ 2 hours)	Visit PBRC to receive free box of FV and receive follow up intervention/reinforcement.
8-15*	Week* following V3	Interventionist will check in with ppt goals and will send group specific nudges via participant's preferred form of communication between V3 and V4.
16*	Visit 4 ~ +7* days from V3 (~ 2 hours)	Visit PBRC to receive free box of FV and receive follow up intervention/reinforcement.

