H1a: FV acquisition, consumption, and diet quality will increase in the control group featuring a reduction in the effective price of fresh FV and

H1b: Food waste will increase in the control group featuring a reduction in the effective price of fresh FV,

where the effective price of fresh FV is reduced via free FV provision (the pick-up site is centrally located with free parking and convenient for most Baton Rouge area residents). According to Hamilton and Richards (Proposition 1) if food waste reduction knowledge (θ) is increased then the amount of fresh food consumed will increase while the amount wasted will decline so long as $F > 1 - \gamma$, i.e., so long as demand for fresh food is not too price elastic. Hence, we forward:

H2a: FV acquisition will increase in the treatment group featuring both a reduction in the effective price of fresh FV and a smart intervention to reduce food waste,

H2b: FV consumption will increase without increasing total energy intake and diet quality will also increase in relation to the control group, and

H2c: Food waste in the treatment group will be less than food waste in the control group.

Expected Outcomes

We expect to assess whether programs that subsidized FV acquisition are efficiently translating program dollars into improved nutrition rather than into increased energy intake and increased FV waste and to develop interventions that ensure funds targeted

to increase household FV acquisition are efficiently translated into improved household nutrition. We will:

1. Assess the impact of free FV provision on FV intake and household food waste production
2. Measure the efficacy of the smart intervention
3. Provide insights to guide future policies and interventions that target increased FV consumption through free or subsidized FV provision.

We also expect to improve upon the efficiency of the FoodImage app through continual assessment of participant feedback and by improving the efficiency of image analysis and data input.

Study Endpoints

Primary analysis objectives follow the hypotheses, which we are sufficiently powered to assess:

- 1) Quantify baseline distributions:
 - a. Mass (g), energy (kcal), and macronutrients (g and kcal) for household food waste levels, food purchasing patterns, food intake, and consumption of FV including beginning FV inventory, total FV acquisition, and total FV intake

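### A storage clean-out is asked for before the baseline waste window but none is described before follow-up, so the Toss part of the control-arm before-after test of H1b is not like for like

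*Combined protocol and SAP*

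**What the plan says.** **Before baseline.** Procedures (Visit 1) says that, to prepare for home recording, "participants will be asked to clean out their fridge, freezer and cabinets of any items that need to be discarded". The FV inventory comes next: "After the cleanout is conducted, the participant will complete a video home inventory of all fruits and vegetables". The Schedule of Procedures puts that inventory on Day -8, the day of Visit 1, and the recording in the week from Day -7 to Day -1. Baseline recording covers Shop, Prep, "intake (Eat) and waste (Toss) for approximately 3 (24 hour) days; ideally including 1 weekend date".

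**Before follow-up.** "In the week following Visit 4 participants will continue intervention, consume their last box of fruit and veg", and they record the same four streams for about three days. The video inventory is repeated the day before Visit 5. No clean-out instruction appears. Between Visit 2 and the end of the study, storage clean-outs are logged in Toss as they occur; none is scheduled.

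**The test.** Objective 1 says: "We will test these hypotheses by comparing baseline and follow-up data from participants randomly assigned to the control condition". Both arms receive the FV box. H1b states: "Food waste will increase in the control group featuring a reduction in the effective price of fresh FV". The document does not say whether items discarded in the pre-baseline clean-out are logged, weighed or added to baseline waste, and it describes no adjustment for them.

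**The concern.** The clean-out removes, just before recording starts, the stored food most likely to be thrown away in the next few days. The follow-up window opens on a store that has had no such instruction. Even if household behaviour never changed, the Toss component could differ between the two windows.

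A comparison between arms would cancel such a difference. H1b has no comparison arm: it is a within-arm change, and no group goes without the box. An artefact of the recording procedure would therefore be read as an effect of free FV. The same contrast also carries recording reactivity, calendar effects and the stress coaching, yet Objective 1 presents it as a test of what free provision does. Expected Outcome 1 repeats that claim and Expected Outcome 3 offers guidance for subsidy policy, so a false finding that free produce raises waste would matter.

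**Working it through.** **Inputs.** From Power analysis: SD of change in waste 295 g, group difference 298 g, earlier control-arm change -33 g, and 23 or 20 households per arm. Assumed: two-sided 5% (the plan gives no alpha) and a paired t-test for H1b (the plan names no test). The documents give no size for the clean-out effect, so a range is used.

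**The plan's own figure.** Effect size = 298/295 = 1.01. The two-sample t-test has noncentrality 1.01 × √(n/2).
- n = 23 per arm: power 0.918 (stated 0.92).
- n = 20 per arm: power 0.875 (stated 0.88).

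Both reproduce, which supports the two-sided 5% assumption.

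**H1b with no true effect.** Let b be the net artefact in the mean control-arm change.
- Standard error = 295/√n: 61.5 g (n = 23), 66.0 g (n = 20).
- Critical t: 2.074 (22 df), 2.093 (19 df).
- Smallest significant mean rise: 2.074 × 61.5 = 128 g; 2.093 × 66.0 = 138 g.
- Chance of a false significant increase = P(T > critical t), where T is noncentral t with noncentrality b/SE. For b = 100 g and n = 23, the noncentrality is 100/61.5 = 1.63.

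| Net artefact b | n = 23 | n = 20 |
|---|---|---|
| 0 g | 2.5% | 2.5% |
| 50 g | 11.9% | 10.8% |
| 100 g | 34.3% | 30.1% |
| 150 g | 64.5% | 57.9% |

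The benchmark is 2.5%, not 5%, because only the upper tail supports H1b.

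**Offsetting drift.** If the earlier control-arm change of -33 g recurred, a 100 g clean-out artefact would leave 100 - 33 = 67 g net. The chance of a false increase at n = 23 would then be 17.9%. For 50 g (17 g net) it would be 4.5%.

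**Sign.** The table assumes the discarded items are outside baseline waste, so that baseline is too low. If they are counted, baseline is too high, b is negative, and a true increase could be masked.

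**H2c.** Baseline precedes randomisation and both arms follow the same procedure, so a common shift cancels. Simulated type I error of the between-arm test with 23 per arm, for shifts of 0, 100 and 200 g in both arms, was 5.0%, 5.1% and 5.0%.

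**The case against.** Several points on the other side have weight.

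- **The missing follow-up clean-out is inferred from silence.** The Schedule of Procedures does not list the baseline clean-out either, so its silence at follow-up shows nothing. The asymmetry rests on the narrative alone, which repeats the recording and the inventory but not the clean-out. This stands as a caveat.
- **The direction is not settled.** Background describes Toss as covering refrigerator and cabinet clean-outs, and the app is installed at Visit 1, so participants could log the discarded items. The Day -8 timing favours their exclusion, but no text says so. This stands, and it is why the point is stated both ways.
- **The clean-out has a purpose.** It clears backlog from before the study that might otherwise fall inside the first window. That is a fair reason for having it, but it does not make the two windows alike.
- **The grams are free choices.** The SD comes from weekly waste at meals in an earlier study, not from a three-day total that includes storage discards. The table is an illustration, not an estimate.

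A reader might infer that the whole of H1 is biased. The documents do not support that: the clean-out bears on stored-food discards, and H1a (acquisition, consumption, diet quality) is not clearly affected. A reader might also infer that the two FV inventories cannot be compared, or that the baseline-to-follow-up correlation is weakened. The first is too strong, since only items due for discard are removed and staff guide both inventories. Nothing in the documents supports the second.

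**Conclusion.** The point holds for the Toss component of H1b. As written, the baseline and follow-up windows differ in procedure, the test has no comparison arm to absorb the difference, and the plan has no rule for the discarded items. Under the likelier reading, that these items are outside baseline waste, the clean-out pushes the change toward the hypothesis.

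How far is unknown. Net artefacts of 50 to 150 g would raise the chance of a false significant increase from 2.5% to between 12% and 64% with 23 households (11% to 58% with 20). This rests on the borrowed 295 g SD, a paired t-test and two-sided 5%. It would be tempting to conclude that H1b is bound to come out positive. The documents do not support this, because drift such as the earlier -33 g works the other way and the net bias cannot be signed.

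The randomised waste comparison, H2c, and its stated power of 0.92 and 0.88 are not affected. Apart from the clean-out, a before-after change in one arm cannot carry the causal wording of Objective 1. That applies to H1a as well as H1b.

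**What to change.** 1. State that items discarded in the pre-baseline clean-out are excluded from the baseline waste total, and record them separately.
2. Report H1b also on Prep+Eat waste alone, which leaves out the storage discards that the clean-out alters. State that this analysis cannot show whether stored FV spoil. Report Toss waste logged from Visit 2 onward descriptively beside it.
3. Reword Objective 1, H1a, H1b and Expected Outcome 1 as the before-after change in households given the FV box plus stress coaching, not as the effect of free FV provision.

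A matching clean-out at Visit 4, kept outside the window total, looks like the natural repair but should not be added. It would remove spoiled produce from the earlier boxes, which is part of the waste that H1b and H2c are meant to measure.

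The cost is a separate record of the clean-out items, one extra analysis with a descriptive summary, and a weaker claim for Objective 1.

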Finally, the FoodImage app, and its data collection methodology, integrates customizable notifications and reminders to remotely prompt participants to record data, resolve data collection problems, etc. These notifications and reminders utilize Ecological Momentary Assessment (EMA) methodology¹¹ to maximize data collection protocol adherence by reminding participants to capture and send food information at relevant times. This notification functionality of FoodImage can also be leveraged to communicate information about ongoing interventions and can facilitate adherence to dietary changes and strategies to reduce food waste.

Increasing household FV consumption while reducing food waste requires behavior to change in two overlapping domains, each of which has been the focus of considerable work^{7 12}. Current efforts to change household level behavior are often compartmentalized, focusing either on increasing FV consumption or reducing food waste, but not on the behaviors together. In doing so, existing interventions fail to consider the linkages between behaviors that occur in households and may affect positive change in one domain with negative or neutral impacts on the other domain (e.g., increase FV consumption but increase food waste or reducing food waste by limiting fresh FV consumption). Hence, it is essential to articulate any unintended consequences that existing programs present across these two domains and create interventions that simultaneously promote behavior change that advance both goals.

Methods

Study Design

We will conduct a randomized controlled trial (RCT) featuring two groups that both receive free boxes of FV. The box of fresh FV will contain about 40% fruit and 60% vegetables and be sufficient to meet 60 ±5% of the household's FV needs as recommended by USDA's MyPlate. The amount of FV provision will scale in proportion to the size of the household as is done with SNAP benefits (as noted earlier, it is estimated that ~20% of participants will actually be eligible for SNAP). The groups differ in the intervention provided, with the treatment group receiving a smart intervention to reduce food waste and replace consumption of less healthy foods with FV and the control group receiving an intensity-matched intervention focused on an unrelated topic (stress management).

Participants

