Data from the FoodImage app will be prepared for analysis using methods detailed in [name] et al. (2020)¹. Briefly, images captured through the app are viewed by PBRC's nutrition staff who identify nutrient matches using Standard Reference (SR) 28 and the Food and Nutrient Database for Dietary Studies (FNDDS) 6.0¹⁴ (USDA 2020b)¹⁵ and estimate the mass of portions of food acquired, prepared, selected, consumed, returned, and discarded at each stage. Specifically, we will obtain mass (grams), energy (kilocalories), and macronutrients for shop, prep, eat, and toss occasions. The SR database provides inedible percentages. Furthermore, for all foods except raw meats where the SR database is used, we will obtain highly granular data. The FNDDS database translates whole food items into FPED values which converts each consumed food and beverage into the 37 USDA Food Patterns components¹⁶. The FPED values are used to assist in the quantification of diet quality (HEI) and to guide healthy food intake patterns (e.g., the 'five a day' campaign to promote FV consumption). The Food Patterns are measured as cup equivalents for fruits and vegetables. Thus, we can examine the number of servings of fruits, vegetables, dairy, grains, and proteins (each of the food groups) consumed. Also, we will examine diet quality in relation to the USDA Dietary Guidelines for Americans with the HEI¹⁷. During the two ≥ 3 -day intensive collection windows, participants record the source, reason and destination of all food waste on the app, which is attached to each data point. Receipts associated with food acquisition, which are collected for all 28 days, are processed via Optical Character Reader (OCR) with resulting price data checked for accuracy by human raters.

The method proposed by Pocock and Simon¹⁸ will be used for intervention assignment to minimize imbalance among factors that might be associated with outcomes of interest. Specifically, randomization will be adaptive according to the values of the Aitchison distance calculated using the following prioritized drivers of FV consumption and food waste: 1) the presence of children in the home vs. no children, 2) SNAP eligibility vs. being ineligible, and 3) the presence of a fruit tree and or garden at the home vs. the absence of these amenities. Greevy et al.¹⁹ the sample size required for achieving the same power is often reduced if factors associated with the outcomes are balanced among the intervention groups.

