 - b. FPED values, i.e. serving size, for food intake and consumption of FV including FV inventory, total FV acquisition, and total FV intake
 - c. Quantify baseline diet quality (i.e. food intake as assessed by the HEI)
- 2) Determine how the smart intervention altered:
 - a. Mass (grams), energy (kcal), and macronutrients (g and kcal) for household food waste levels, food purchasing patterns, food intake, and consumption of FV including FV inventory, total FV acquisition, and total FV intake
 - b. FPED values, i.e. serving size, for food intake and consumption of FV including FV inventory, total FV acquisition, and total FV intake
 - c. Quantify diet quality (i.e. food intake as assessed by the HEI)
 - d. Acquisition and intake of non-FV foods
 - e. The percent of household food waste that was FV

Secondary analysis objectives include assessing the demographic (e.g., age, education), household (SNAP eligibility, household size, beginning food inventories), and attitudinal factors (e.g., frugality, health and environmental consciousness) related to the primary analysis targets.

Power analysis

Power analysis was conducted for change in the primary outcome variable (grams [g] of food waste) from baseline to the end of the intervention to detect significant differences between treatment and control groups. Following the methods of our previous study, waste data will be summarized and analyzed by aggregating across measurement days. Based on weekly data from our previous study, the participants in the group receiving a smart food waste reduction intervention reduced their waste at meals by 331 g while the control group only reduced their waste by 33 g (298 g group difference), while the pooled standard deviation of the change in food waste between the control and treatment groups was 295 g, yielding an effect size of 1.01. The power to detect an effect size of 1.01 is 0.92 if there is no attrition (23 per group) and is 0.88 if attrition exceeds the 10% expectation (20 per group or 13% attrition). Given the power analysis is based upon an RCT that did not involve the provision of free FV, we expect effect sizes to be larger in the proposed study due to the presence of free FV, yielding even higher power than projected above.

Provisions to Monitor the Data to Ensure the Safety of Subjects

Adverse events will be monitored at each intervention visit. The PI and his co-investigators will review all data continuously to ensure the safety of each subject.

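### The allocation rule rests on an Aitchison distance over three yes/no factors with no composition or zero rule given, so early assignments cannot be made as written, and the design table describes a different scheme

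*Combined protocol and SAP*

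**What the plan says.** The protocol describes allocation in two places.

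- **Analysis section.** It begins with a standard method: "The method proposed by Pocock and Simon¹⁸ will be used for intervention assignment to minimize imbalance among factors". The next sentence makes this operational: "randomization will be adaptive according to the values of the Aitchison distance calculated using the following prioritized drivers". All three drivers are yes/no features of the household: whether any children live there, whether it qualifies for SNAP, and whether it has a garden or fruit tree. The section then argues that balance on such factors can reduce the sample size needed.
- **Design table under Objectives.** Here assignment is at random inside matched pairs, with 23 control and 23 treatment participants.

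The Procedures text for Visit 2 only refers the reader to the Analysis section. Study Design gives the one available prevalence: "it is estimated that ~20% of participants will actually be eligible for SNAP". The Power analysis section relies on equal arms: "The power to detect an effect size of 1.01 is 0.92 if there is no attrition (23 per group".

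Nowhere does the protocol state which composition enters the distance, how zero counts are treated, how the priority order becomes weights, the probability of assigning the favoured arm, the tie rule, or any term for overall arm size.

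**The concern.** The Aitchison distance is the Euclidean distance between centred log-ratios of strictly positive parts. Two properties follow from the definition. A zero part leaves it undefined, and multiplying every part by a constant leaves it unchanged. Binary factors in a trial of 46 produce empty categories early on, and invariance to totals is unwelcome in a rule meant to deliver two equal arms.

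At stake is whether the allocation can be reproduced and audited. Two programmers given this text could code different rules, and both would have to invent a step for the first participants. Random allocation supports H2c, the between-group food-waste comparison on which the power calculation is based. The design table adds a further scheme that does not agree with adaptive minimisation.

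**Working it through.** **Inputs.** From the protocol: N = 46; 23 per group; difference 298 g; SD of change 295 g; SNAP eligibility about 20%. Assumed: two-sided alpha 0.05; children 40% (range 30–50%); garden or fruit tree 30% (range 20–50%); favoured-arm probability 0.8 or 1.0; 0.5 added to counts so that the distance exists.

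**The plan's own figure.** d = 298/295 = 1.01. A noncentral-t calculation gives power 0.918 at 23 per arm and 0.875 at 20 per arm. The stated 0.92 and 0.88 both reproduce.

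**Zeros.** With SNAP at 20%, the chance that at least one arm has no eligible household at n per arm is 1 − (1 − 0.8ⁿ)²:

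- n = 1: 0.96
- n = 5: 0.55
- n = 10: 0.20
- n = 23: 0.01

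Across all three factors (40/20/30%), a median of about 11 to 14 of the 46 assignments are made while some arm-by-level cell is empty. If the composition is the joint eight-cell table, the distance is undefined at essentially all 46. If only the new participant's own levels matter (the within-level split), zeros arise on about 5 to 6 early steps checking one trial placement, and about 7 checking both.

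**Totals.** For two-part compositions a:b and c:d the distance is the absolute value of ln(a/b) − ln(c/d), divided by √2. Counts 6:4 and 18:12 give ln 1.5 − ln 1.5 = 0, so arms of 10 and 30 score as perfectly balanced.

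**Household-level reading.** The matched-pairs row makes this reading possible. With 0/1 coding, any household lacking a factor has an undefined distance. With 1/2 coding:

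- (1,1,1) to (2,2,2), which differ on all three factors: 0
- (1,1,1) to (2,1,1), which differ on one: ln 2 × √(2/3) = 0.566
- (2,1,1) to (1,2,2), which differ on all three: ln 2 × √(8/3) = 1.132

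The value therefore depends on the coding, and opposite households can score as identical.

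**Arm sizes.** Sequential allocation of 46 participants was simulated at 40/20/30%. The coin-toss tail is exact: 2·P(X ≤ 19) with X ~ Bin(46, 0.5) = 0.30.

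| Rule | Difference of 8 or more | Mean power |
|---|---|---|
| Factor mix of each arm, probability 0.8 | about 45% | 0.904 |
| Factor mix of each arm, deterministic | about 75% | 0.807 |
| Arm split within level, 0.8 or deterministic | about 0% | 0.917–0.918 |
| Marginal counts (Pocock-Simon), 0.8 or deterministic | about 0% | 0.917–0.918 |
| Coin toss | about 30% | 0.912 |

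Over the assumed prevalence range, the factor-mix reading gives mean power of about 0.90–0.91 at 0.8 and 0.79–0.82 if deterministic. Under the within-level split, the smaller arm is at least 22 in 95–100% of runs.

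**Power by split.** 23/23 0.918; 26/20 0.913; 29/17 0.899; 33/13 0.855; 36/10 0.789.

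**The case against.** The strongest reply is that the distance elaborates a sentence naming Pocock-Simon, which works on arm counts within factor levels. Read that way, the composition is the arm split within each level, arms stay near 23, and power is unaffected. A small offset, or simple randomisation for the first few participants, makes the distance computable. Moderate imbalance costs little: 0.913 at 26/20 and 0.899 at 29/17, both above the 0.88 the plan accepts under attrition. Unequal arms do not by themselves bias the comparison.

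Most of this stands, and it limits what can be claimed. A reader might infer that the stated rule cannot hold 23 per group. The documents do not support that: it follows from the factor-mix reading, and the protocol does not choose a reading. A reader might also infer that the stated power is wrong. It reproduces, and it is materially threatened only by severe imbalance. Nor is the distance beyond repair at zeros; what is missing is a zero rule.

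The reply does not remove the point. Every reading examined meets zeros that the text does not address. An offset would leave arm size uncontrolled on the factor-mix reading. None of this reconciles the Analysis section with the matched-pairs row.

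**Conclusion.** The point holds as a fault of specification, made worse by an ill-suited metric. As written, the early assignments cannot be made without improvising, and the two descriptions of allocation conflict. Loss of arm-size control is conditional. On the factor-mix reading control is worse than a coin toss (about 45% against 30% for a difference of 8 or more at probability 0.8), with mean power about 0.90, or about 0.81 if deterministic. On the within-level reading nothing is lost. These sizes rest on the assumed prevalences for children and garden, the assignment probability, the 0.5 offset and two-sided alpha 0.05. The zero problem and the indifference to totals follow from the definition of the distance. This should be fixed, but it does not show that the trial's power or validity has failed.

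**What to change.** Replace the Aitchison distance with the marginal-count score of the method already cited. For each trial placement of the new participant, sum over the three factors the absolute difference in arm counts at that participant's level, and add the absolute difference in arm totals. Assign the arm with the lower score with a fixed probability below 1 (for example 0.8) and break ties at random. If the priority order is meant to matter, state the weights.

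Correct the matched-pairs row in the design table to agree. If enrolment has begun, apply the rule from the next participant and record the date.

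This score is always computable. Even without the arm-total term, it kept the smaller arm at 22 or more in about 95% of simulated trials at probability 0.8 and in all of them when deterministic, with mean power 0.917–0.918. The cost is one protocol paragraph, one table row and minor reprogramming; no participants, visits or data are added.
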